Data analyses: Our study is descriptive and exploratory. Since we recruited 94 women ≥ 75 years from 46 PCPs in the first year of our DA trial, we feel our recruitment goals are feasible. We will report how many PCPs found prognostic information useful and helpful, and facilitators and barriers to using prognostic information when discussing stopping cancer screening. Using chi-square tests, we will examine if PCP experiences differ by their sex or practice site (BIDMC/APG). With 45 PCPs we will have limited power for these analyses; however, we will explore if there is a direction of effect. We will also report how many patients reported that their PCP discussed stopping cancer screening and/or their prognosis and patients' perceptions of these discussions. We will use chi-square statistics to examine if there are differences in patient preferences or experiences by their sex, age, or practice site. For example, with 100 patients and assuming that 50% are female (n=45), at an alpha of 0.05, we will have 0.81 power to detect a 28% difference in preferences for prognostic discussions by patient sex. While we will have limited power to detect small differences in patient characteristics around preferences for prognostic information, we will examine if there is a direction of effect. We will also examine if patients' intentions to be screened (measured on a validated 15 point scale)⁹⁵ change after seeing their PCP using the Wilcoxon Signed Rank Test. In our decision aid trial, we have recruited 196 women ≥ 75 years with <10 year life expectancy. At baseline, their mean intentions to be screened with mammography on the 15 point scale was 3.7 (+/-4.9), indicating that on average they were strongly leaning towards being screened. Therefore, if we assume in this study that we will have at least 40 female participants with complete data (accounts for 5 women missing data) and that the within pair correlation is as low as 0.1 (however, we expect a higher degree of correlation and therefore higher power), we will have 0.87 power to tell a difference in a mean score of 3.7 before the PCP visit and a mean score of 7 (being unsure about screening among participants on average) after

the PCP visit if the standard deviation is also 4.9. In sensitivity analyses, we will examine if there is a clustering effect by PCP. We anticipate greater power to examine differences in intentions to be screened for CRC since both sexes are screened for CRC.

C. Subject Selection

Patient Eligibility: To target patients with 5-10 year life expectancy and for whom a discussion about stopping screening would be appropriate, we will recruit patients aged 76-79 with at least one Charlson Comorbidity⁷³ and all patients 80-89 years that meet eligibility criteria. Charlson comorbidities include: myocardial infarction, congestive heart failure, peripheral vascular disease, cerebrovascular disease, emphysema/COPD, connective tissue disease, peptic ulcer disease, diabetes, hemiplegia, leukemia, malignant lymphoma, solid tumors, liver disease, chronic kidney disease, and HIV or AIDS.⁷³ Since the average life expectancy of a 75 year old man is 11.0 years and a 75 year old woman is 12.9 years,⁷⁴ by necessitating that a patient 76-79 years has a Charlson comorbidity we will increase the likelihood that study participants will have <10 year life expectancy.⁷⁵ The average life expectancy of an 80 year old man is 8.2 years and is 9.7 years for an 80 year old woman.⁷⁴ We chose to limit our sample to patients 76-89 years because regardless of life expectancy the USPSTF does not recommend breast or CRC screening for adults >75 years and a discussion about stopping cancer screening would be appropriate for these patients. Although approximately 20% of adults 65-75 years have <10 year life expectancy, some PCPs may feel uncomfortable recommending stopping screening to these patients since guidelines recommend screening these patients based on their age.^{4, 76} To target patients who have been engaged in cancer screening, we will include women who have undergone mammography screening in the past 3 years and women and men that have undergone CRC screening in the past 10 years but for whom there is no documentation in the screening sheet or problem list that the patient has chosen to stop being screened for cancer. We will exclude patients with a history of breast and/or colon cancer; patients whose last colonoscopy showed adenomatous polyps; and women whose last mammogram was read as abnormal since screening decisions may differ for these patients. To further exclude patients who have already decided to stop being screened, we will ask patients their intentions of being screened for breast (women only) or CRC cancer using a validated measure (scored from 1-15), and we will exclude those who score 11-15 (leaning towards not being screened) for both cancers (women) or CRC cancer (men). We will also exclude patients who do not speak English, are in hospice, do not have capacity to participate, have a history of dementia or score ≥ 10 (indicative of dementia) on the Orientation-Memory-Concentration (OMC) test.^{77, 78} To determine capacity, we will ask patients 7 institutional review board (IRB) approved questions (see Appendix A1 for the eligibility questionnaire) about their understanding of the study, the benefits and harms, and their role. We will exclude patients who answer 3 out of 7 questions incorrectly. We plan to include adults with capacity for informed consent but with mild cognitive impairment (MCI, suggested by scores of 5-9 on OMC test) since: 1) ~20% of US adults ≥ 75 years have MCI;⁹⁶⁻⁹⁸ 2) many are screened without discussion of the risks of cancer screening and/or the lag-time to benefit;⁹⁹ 3) MCI increases with age and is associated with comorbidity and shorter life expectancy;¹⁰⁰ and 4) adults with MCI have successfully participated in our previous studies.¹⁰¹ We are excluding patients with dementia because we are interested in learning from patients how their PCP may discuss their prognosis when talking about stopping cancer screening. As a next step, we plan to develop strategies for PCPs to discuss prognosis with older adults with dementia and their proxies. Since on average adults ≥ 90 years have <5 year life expectancy⁷⁹ and since dementia is common (36%) we will exclude adults ≥ 90 years.⁸⁰ We will target a sample that is 50% female and socioeconomically diverse.

In addition, if a patient would like a family member aged ≥ 21 years to be present during individual interviews, we will welcome the family member to consent and participate in the interview. Patients that participate in Aim 1 will not be eligible to participate in Aim 2.

PCP Eligibility: We plan to recruit PCPs to this study from HCA, Senior Health, and from up to 16 Boston area community primary care practices that make-up BIDMC's Affiliated Physician Group

(APG). Non-resident physicians and nurse practitioners that care for a patient panel that includes adults >75 years will be eligible. We will exclude clinicians that only see patients for urgent care.

No participant will be excluded based on race, ethnicity, or sex. Participants of all races and ethnicities will be sought. We plan to study English-speaking patients since we are exploring a novel topic- how PCPs should approach discussions about patient prognosis when recommending older adults stop being screened for cancer. Once we develop strategies for PCPs to use when talking to older adults about their prognosis in English, we will translate these strategies to other languages to learn if they are acceptable to non-English speaking older adults.

B4. POSSIBLE BENEFITS

All patient participants will receive \$25 compensation for participating and PCPs will receive \$50 compensation for participating. More generally, we will learn from patients and PCPs how PCPs may approach the topic of patient prognosis when discussing stopping cancer screening with older adults. If PCPs and patients become more comfortable talking about prognosis, older adults may be provided with the information they need to make higher quality decisions about whether or not to undergo cancer screening and other medical tests and interventions. Also, if PCPs learn to discuss prognosis with older adults when patients have close to 10-year life expectancy it could lead to earlier discussions between PCPs and older adults about advanced care planning and goals of care that may lead to improved care of older adults near the end of life. Although guidelines recommend that PCPs not screen older adults with <10 year life expectancy for breast or colon cancer, many older adults with short life expectancy are screened and few understand that the benefits of screening take years to occur while the chance of harm is immediate.^{9, 10} Making information about patient prognosis accessible to PCPs and providing PCPs with guiding principles and language on how to discuss prognosis with older adults will hopefully lead to better clinical decision-making and improved care of older adults. Ideally, by better understanding their prognosis, older adults with short life expectancy may avoid tests from which they are unlikely to benefit and may only cause harm. Since the research proposal only involves interviewing older adults and PCPs, providing PCPs with patient prognostic information, and reviewing patient medical records, this study poses minimal risks to participants. The risks to subjects are reasonable in relation to the anticipated benefits to subjects and others.

B5. POSSIBLE RISKS AND ANALYSIS OF RISK/BENEFIT RATIO

This study involves reviewing patient medical records, conducting individual interviews and focus groups with patients and interviewing their PCPs, recording interviews, and providing PCPs with information on their patients' prognosis. It poses very little risk to participants. Some participants may develop feelings of anxiety, distress, or fatigue when answering interview questions. We will inform participants that they may stop interviews at any time, skip any question that makes them feel uncomfortable, and/or withdraw their participation. PCPs who prefer not to talk in front of other individuals will be offered the opportunity to participate in an individual interview instead of a focus group. Questionnaires for Aim 2 are shorter in length than questionnaires that we have used successfully in prior studies.¹⁰²⁻¹⁰⁴ The information we are giving PCPs on patient prognosis may be estimated using calculators available on the web; however, we are making the information easily accessible to PCPs. If a PCP chooses to discuss prognosis with a patient, it is possible the patient may get upset; however, this is what we are trying to learn in this study- how to talk to older adults about their prognosis in a patient-centered non-threatening way that improves the patient-doctor relationship. Studies conducted with patients with serious illnesses near the end-of-life find that patients want the truth about their prognosis and that patients are not harmed when their clinicians talk to them about their prognosis.^{40, 49, 50} The utmost respect will be paid to participant privacy and interviews and focus groups will be conducted in private. Data will be entered as it is collected into REDCap, so there will not be paper records. Each participant will be given a unique study ID not associated with personal identifiers to link with their data. Data used in analyses will be de-identified. All audio tapes will be coded so that no personally identifying information is visible on them; they will

be kept in a locked file cabinet in the investigator's office; they will be heard only for research purposes; and they will be destroyed in compliance with NIH policy. Each participant will have usual access to their PCP and [name] will also be available to talk with participants if they feel anxious.

B6. RECRUITMENT AND CONSENT PROCEDURES

Patient Recruitment and consent: Recruitment of patients to this study is similar for Aims 1 and 2. Through a HIPAA waiver, in Aim 1, we will have a data manager provide a list of all patients aged 76-89 seen at each site in the past year stratified by patient race and sex. In Aim 2, we will ask the data manager to produce a similar list; however, we will ask that the list only include patients aged 76-89 that are scheduled to be seen by a PCP participating in Aim 2 in the next 4-12 weeks. Also, in Aim 2, we will ask the data manager to send us an updated patient list every two weeks so that we will continuously have new patients that we may screen for eligibility that are scheduled to see their PCP. After obtaining the list of patient names, we will review patient records sequentially to find patients that meet our eligibility criteria. We will email the PCP of potentially eligible patients to ask permission to contact their patients and attach the opt out letter (Appendix C.3) that we plan to send to patients to this email. We will inform PCPs that our study aims to understand how patients would like their PCP to discuss their prognosis when discussing stopping cancer screening. We will ask PCPs to exclude patients with dementia or that are non-English speaking. We will send patients deemed eligible by their PCP an informational letter about the study (see section E.2.a below for more information about the contents of the Aim 1 and Aim 2 informational letters). The informational letter will include a number to call if patients want to opt-out of being contacted. After one week, the research assistant (RA) will call patients who have not opted-out to further describe the study and to see if they are willing to participate. For patients willing to participate, the RA will re-establish eligibility. Once a patient is willing and eligible to participate, the RA will follow the procedures described below specific to each aim.

Aim 1: In Aim 1, the RA will ask patients willing and eligible to participate in an individual interview. If the patient is willing to participate we will schedule to meet him/her at a time and place that is convenient for the patient (e.g., clinic, the patient's home). We will obtain written informed consent. If a patient would like a family member to be present at the individual interview, we will also obtain written informed consent from the patient's family member. We will offer participants \$25 incentive.

Aim 2: For Aim 2, if a patient is willing and eligible to participate, the RA will schedule a time convenient to the patient to complete the background questionnaire over the telephone. The RA will obtain verbal informed consent in Aim 2 rather than written informed consent because this is a minimal risk study and we do not plan to audio-record interviews in Aim 2.

For both Aims 1 and 2, we will offer patient participants \$25 incentive for participating. [name] has successfully used these recruitment methods and incentives in prior studies.^{14, 104}

PCP Recruitment and Consent: [name] will invite PCPs to participate in Aims 1 and 2 through individual emails and through in person presentations at faculty meetings. PCPs that participate in Aim 1 will be permitted and invited to participate in Aim 2 since in Aim 2 we will be collecting information from PCPs at the point of care about their experience with a patient. We will provide PCPs a \$50 incentive for participating. Table 1 shows the number of PCPs at each practice. We aim to recruit 48 eligible PCPs to participate in Aim 1 and 45 eligible PCPs to participate in Aim 2.

Aim 1: For Aim 1, we will explain to PCPs that we are conducting focus groups and individual interviews to learn from PCPs how best to approach talking to older adults about stopping cancer screening and their long-term prognosis. We will explain that we anticipate that the focus group will take one hour and that we will provide a meal. We will ask focus group PCPs to come 15 minutes early to complete written informed consent, to complete a questionnaire on their background characteristics, and to enjoy the meal. The email will also inform PCPs that we will provide \$50 incentive for participating. The written informed consent form will explain that we aim to better

understand how to discuss prognosis with older adults when discussing stopping cancer screening, that we anticipate 48 PCPs will participate in 5 focus groups, that the study involves participating in a focus group or individual interview and completing questions about their background characteristics, and that participants will receive \$50 in appreciation of their time. If a PCP responds that they would like to participate but cannot attend or would prefer not to participate in a focus group then we will offer that PCP to participate in an individual interview. If a nurse practitioner (NP) responds that s/he would like to participate in a focus group then we will let the NP know that we plan to ask him/her to stay for a few minutes after the focus group for an exit interview focused specifically on the NP role in discussing stopping cancer screening and long-term prognosis with older adults. The consent form will also explain that the interview will be recorded and how recordings will be stored and protected. It will also explain that participation is voluntary, that they may withdraw their participation at any time, and that their decision to participate will not affect their relationship with any member of the research team or any other individuals at BIDMC.

Aim 2: For Aim 2, we will present the study at faculty meetings and we will email PCPs individually to inform them of the study and to ask them to participate. The email will inform PCPs that we are interested in learning if information on their patients' prognosis is useful to them when discussing cancer screening with adults >75 years. We will explain that we will attempt to recruit up to 5 of their patients to participate. Each time one of their patients chooses to participate, we will email the PCP (through secure email) their patient's prognosis calculated by the Lee-[name] index and we will send a copy of Cho et al.'s US life tables that provides information on older adults' life expectancy by age stratified into quartiles (see Appendix A.9. for a draft of the information we will provide).⁸ After their 5th patient participates or at the end of the study, depending on which comes first, we will ask PCPs to complete a 10 minute web-based questionnaire about their experience. We will inform PCPs that they will receive \$50 in appreciation for their time for participating in this study. The email will also explain to PCPs that their participation is completely voluntary; that they can withdraw their participation at any time; and that if they decide not to participate in the study their decision will not affect their relationship with the research team or any other individual at BIDMC or APG. The email will also inform PCPs that their responses to questionnaires will be confidential and will be analyzed using a unique study ID.

Financial Planner/Clergy Recruitment and Consent: [name] will invite financial planners/clergy to participate in Aim 1 through individual emails. We will provide financial planners/clergy a \$50 incentive for participating. We aim to recruit 5 financial planners and 5 members of the clergy to participate in Aim 1.

Aim 1: For Aim 1, we will explain to financial planners/clergy that we are conducting individual interviews to learn from financial planners/clergy how best to approach talking to older adults about their long-term prognosis. We will explain that we anticipate that the interview will take 30 minutes. We will ask financial planners/clergy to complete written informed consent and to complete a questionnaire on their background characteristics. The email will also inform financial planners/clergy that we will provide \$50 incentive for participating. The written informed consent form will explain that we aim to better understand how to discuss prognosis with older adults that we anticipate 5 financial planners/clergy will participate in interviews, that the study involves participating in an individual interview and completing questions about their background characteristics, and that participants will receive \$50 in appreciation of their time. The consent form will also explain that the interview will be recorded and how recordings will be stored and protected. It will also explain that participation is voluntary, that they may withdraw their participation at any time, and that their decision to participate will not affect their relationship with any member of the research team or any other individuals at BIDMC.

B7. STUDY LOCATION

Privacy

The utmost respect will be paid to participant privacy. Participant responses and data will be directly and securely stored and password protected via REDCap. Interview recordings will be stored in a locked cabinet in [name] office. All interviews will be conducted in private office space or clinical space, or at the patient's home.

Physical Setting

For Aim 1, the RA will schedule to meet the patient at a time and location (e.g., clinic, the patient's home) that is convenient to the patient to conduct the semi-structured qualitative interview. For PCPs, we will attempt to conduct focus groups at a convenient time (e.g., at a time that is periodically reserved for faculty meetings but when a faculty meeting is not scheduled) or an individual interview at the convenience of the PCP.

Aim 2 will be completed over the phone with patients and through email with PCPs; information obtained from these calls and emails will be stored directly on REDCap.

B8. DATA SECURITY

All participants will be given a study identification number (ID). Only the study ID and not participant names or personal identifiers will be downloaded from REDCap with participant data. The ID code will be stored in secure REDCap files that will not be downloaded. Each computer device used to collect human subjects data will be password protected and encrypted. No personal identifiers will be entered using wireless connectivity. Data will be collected specifically for the proposed research project. The utmost respect will be paid to participant privacy and interviews will be conducted in private. Data will be entered as it is collected into REDCap, so there will not be paper records. Each participant will be given a unique study ID not associated with personal identifiers to link with their data. Data used in analyses will be de-identified. All audio tapes will be coded so that no personally identifying information is visible on them; they will be kept in a locked file cabinet in the investigator's office; they will be heard only for research purposes; and they will be destroyed in compliance with NIH policy. Each participant will have usual access to their PCP and [name] will also be available to talk with participants if they feel anxious.

B9 Multi-Site Studies

Is the BIDMC the coordinating site? Yes No

Is the BIDMC PI the lead investigator of the multi-site study? Yes No

B10 Dissemination of Research Results

At the end of the follow-up interview, we will ask participants if they are interested in receiving the final results from this study. We will explain that it may be several years before the results are available. We will keep record of participants interested in learning the results and will mail those patients a summary of our findings. In the letter, we will reference any publications resulting from the study.

2. [name] BD, [name] GL, Hurria A, Hortobagyi GN, Buchholz TA. Future of cancer incidence in the United States: burdens upon an aging, changing nation. J Clin Oncol. 2009; 27(17): 2758-65.

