Overview: In Aim 1, we will conduct at least five focus groups with PCPs and 8 individual interviews to learn their thoughts, attitudes, and experiences with discussing and estimating older adults' prognosis when recommending stopping cancer screening. In addition, we will conduct 30 semi-structured qualitative interviews with adults 76-89 years with approximately 5-10 year life expectancy to learn their thoughts, feelings, and experiences with respect to discussing their prognosis with their PCPs. In addition, we will attempt to interview 5 financial planners and 5 members of the clergy to learn their approach to talking about life expectancy with older adults and the language that they use. We will use data gleaned from these interviews to develop strategies and guiding principles for PCPs to discuss prognosis with their patients when discussing stopping cancer screening and we will draft scripts to suggest language for PCPs to use when having these discussions. Focus groups will be held in an available conference room at BIDMC. Individual interviews will be held in a place that is convenient for the individual, such as available conference room, private office, or private clinic space at BIDMC, or at the patient's home or other private space. In Aim 2, we will learn if PCPs find the scripts and information on their patients' prognosis useful. We will give 45 PCPs (23 community-based) the scripts and patient prognostic information (using the Lee/[name] index and the Walter et al. life expectancy tables) on 1-3 of their patients (goal to recruit 100 patients overall). We will interview PCPs after each patient visit to learn if they found the prognostic information helpful and for feedback on the scripts. We will interview patients after each visit to learn from their perspective if their PCP discussed their prognosis and/or stopping cancer screening and to learn patients' thoughts on these discussions. We will also review the PCP note from the visit to learn if any discussion about prognosis or cancer screening was documented. These data are needed to help PCPs feel prepared to discuss stopping cancer screening and patient prognosis with older adults with <10 year life expectancy.

Aim 1- To learn from PCPs and older adults about how to discuss patient prognosis when recommending stopping cancer screening and to develop strategies for having these discussions.

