PCP recruitment: We will recruit PCPs from the same practices and using the same methods as in Aim 1. PCPs that participate in Aim 1 will be permitted to participate in Aim 2 since we will now be obtaining data from PCPs based on their experience at the point of care. We will explain to PCPs that we are interested in learning strategies for talking to older adults about stopping cancer screening and that we will attempt to recruit up to 5 of their patients to participate. Once one of their patients agrees to participate, we will send the PCP via secure email the patient's prognosis calculated by the Lee-[name] index three days before the patient visit. We will also send PCPs information on patient life expectancy from Cho et al.'s US life tables (see Appendix A9 for an example).⁷⁵ In addition, we will send PCPs the scripts we develop in Aim 1 on how to sensitively include information on patient prognosis when recommending patients stop being screened for cancer. After three of their patients have participated or once we meet our recruitment goals, we will ask PCPs to complete a 10 minute web-based questionnaire about their experience (details below).. We will also offer PCPs to complete questionnaires in person or over the phone if they prefer. We will provide PCPs a \$75 incentive. We aim to have 45 PCPs (1/3 community-based) participate.

Patient recruitment: Patient eligibility criteria and recruitment methods are the same as in Aim 1 except we will only recruit patients with a routine visit scheduled in the next 3-12 weeks with a participating PCP. We will obtain verbal rather than written consent for Aim 2 because we do not plan to audiotape interviews. Also, we will exclude patients that participated in Aim 1. Briefly, we will send patients deemed eligible by their PCP an informational letter about the study. The RA will call patients that do not opt-out of being contacted to reassess patient eligibility and willingness to participate. For patients willing and eligible to participate, the RA will schedule a time to administer the background questionnaire (Table 2 below) before the patient sees his/her PCP. Within 3 days of the PCP visit, the RA will administer a follow-up questionnaire. Patients will receive \$25 incentive for participating. More details on patient recruitment for Aim 2 are in Human Subjects, section E.2.a.

Table 2: Data Collection	When	Content

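### Where power is limited, Aim 2 will look at the direction of a difference with no measure of its uncertainty; report the difference with a 95% confidence interval

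*Combined protocol and SAP*

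**What the plan says.** Section B3.B (Statistical Considerations), under the Aim 2 data analyses, describes the study as descriptive and exploratory. It plans tests for the PCPs: "Using chi-square tests, we will examine if PCP experiences differ by their sex or practice site (BIDMC/APG"). It then says: "With 45 PCPs we will have limited power for these analyses; however, we will explore if there is a direction of effect".

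For patients it plans chi-square comparisons by sex, age and practice site and gives one power example: "we will have 0.81 power to detect a 28% difference in preferences for prognostic discussions by patient sex". It concedes limited power for small differences in patient preferences and adds that "we will examine if there is a direction of effect".

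The section does not define a direction, set a minimum size for one, plan an interval for these differences, or say how a direction will be worded in a report.

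**The concern.** Two observed percentages from small groups rarely tie, so one group will nearly always look higher whether or not the groups differ. Seeing a direction is therefore almost no evidence that a difference exists. When a true difference is small, the sign is also unreliable, and small differences are exactly where the patient clause applies it.

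At stake is the reading of the results. A statement that one sex or one practice setting found the information more useful, given without its precision, can pass for a finding. There are five such groupings (PCP sex and site; patient sex, age and site), each possibly applied to several questionnaire items, so many directions would be available to report.

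**Working it through.** **Inputs from the documents**
- 45 PCPs. The site split is stated in two ways. The B3.A overview says: "We will give 45 PCPs (23 community-based) the scripts and patient prognostic information", which is 22 v 23. The Aim 2 PCP recruitment paragraph says: "We aim to have 45 PCPs (1/3 community-based) participate", which is 30 v 15. Both are used.
- 100 patients. The sex split is unclear: "with 100 patients and assuming that 50% are female (n=45), at an alpha of 0.05". I use 50 v 50 and 45 v 55.
- Alpha 0.05, taken as two-sided.

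**Assumptions.** No response rates or expected PCP differences are given. I take 60% as the common rate under no difference and true gaps of 5 to 28 points otherwise, with one response per person and independent responses.

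**The plan's own figure.** For 50 v 50 patients at 36% v 64%, the null standard error is √(0.5 × 0.5 × (1/50 + 1/50)) = 0.100. The standard error under the alternative is √(2 × 0.36 × 0.64 / 50) = 0.096. Power = Φ((0.28 − 1.96 × 0.100) / 0.096) = Φ(0.875) = 0.81. The same formula gives 0.805 for 45 v 55. The stated 0.81 is reproduced. No power is stated for the PCP comparisons; around a 50% rate, 80% power needs a true gap of about 41 points (22 v 23) or 43 points (30 v 15).

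**How often a direction appears with no true difference.** With X1 and X2 independent binomial counts, P(direction) = 1 − Σ P(X1 = x1) P(X2 = x2) over all pairs with x1/n1 = x2/n2. At 60% in both groups:
- 22 v 23 PCPs: over 99.9%
- 30 v 15 PCPs: 91%
- 50 v 50 patients: 92%
- 45 v 55 patients: about 99%

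The chi-square test rejects in about 5% of the same samples. Across common rates of 50% to 95%, a direction appears in 80% to 100%. Counting only gaps of at least 10 points does not solve the problem: such gaps arise by chance in 54% (22 v 23), 59% (30 v 15) and 36% (50 v 50) of samples.

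**How often the direction is wrong when there is a true difference.** With p1 < p2, P(wrong) = Σ P(X1 = x1) P(X2 = x2) over all pairs with x1/n1 > x2/n2. Ties do not count as wrong.

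| True percentages | Gap | 22 v 23 PCPs | 30 v 15 PCPs | 50 v 50 patients |
|---|---|---|---|---|
| 60 v 65 | 5 | 35% | 33% | 27% |
| 60 v 70 | 10 | 22% | 21% | 12% |
| 50 v 70 | 20 | 8% | 8% | 1.5% |
| 36 v 64 | 28 | 3% | 3% | 0.2% |

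Over mid-rates of 50% to 80%, the ranges for 45 PCPs are 31% to 38% at 5 points, 19% to 25% at 10, 4% to 9% at 20 and 1% to 3% at 28. For patients, over the 45 v 45, 50 v 50 and 45 v 55 splits, they are 23% to 31% at 5 points, 8% to 16% at 10 and at most 2.2% at 20.

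**What an interval would show.** The 95% half-width at 60% is 1.96 × √(0.24 × (1/n1 + 1/n2)):
- 22 v 23: 1.96 × √(0.24 × 0.0889) = 0.286, or 29 points
- 30 v 15: 1.96 × √(0.24 × 0.1) = 0.304, or 30 points
- 50 v 50: 1.96 × √(0.24 × 0.04) = 0.192, or 19 points

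Patients are nested in PCPs (100/45 ≈ 2.2 each). These patient figures ignore that, so true uncertainty may be somewhat larger, above all for comparisons by site.

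**The case against.** The strongest reply is that the plan already says what it is. It calls the study exploratory, keeps a chi-square test for every comparison, attaches a low-power warning to both clauses, and ties no conclusion to a direction. All of that stands. A reader might infer that direction replaces the test, or that it works as a decision rule. The text supports neither: direction is something to be looked at in addition.

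Three further points also stand.
- A reader might infer that the sign is often wrong in general. That holds only for small true gaps. At the 28-point gap in the plan's own patient example, the patient direction is almost never wrong.
- The near-100% figure for 22 v 23 PCPs is partly arithmetic. Groups of 22 and 23 can tie only at 0% or 100%, and at a 60% rate about 22% of no-difference samples differ by under 3 points, which nobody need call an effect. The 30 v 15 split still gives 91%.
- A reader might infer that these directions would decide how scripts are targeted by sex or site. Nothing in the documents says so. Scripts are developed in Aim 1 from qualitative data, with at least one for each cancer type.

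What the reply does not answer is the missing precision. An exploratory label is a reason to report estimates with their uncertainty, and none is planned for these comparisons.

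**Conclusion.** The point holds as a reporting weakness in exploratory comparisons. Where the plan admits limited power, it adds a look at direction that would appear in about 91% to 100% of samples with no true difference (60% assumed in both groups). With 45 PCPs that direction would point the wrong way in about a third of samples at a true 5-point gap and about a fifth at 10 points. For large gaps the sign is reliable, at about 8% wrong for 20 points and 3% for 28. With 50 v 50 patients the error is smaller throughout. The sizes rest on assumed rates and gaps and on independent responses; the conclusion is the same under either PCP site split. The chi-square tests and the stated 0.81 power are not in question here.

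**What to change.** Keep the chi-square tests and both limited-power caveats. Replace only the two clauses about direction with:

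> For each comparison we will report both percentages and their difference with a 95% confidence interval (allowing for clustering by PCP in the patient comparisons), and we will not interpret the direction of a difference without its interval.

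The clustering allowance fits with the sensitivity analysis by PCP that the section already plans. A ban on mentioning direction whenever the interval includes zero would go too far. At 50% v 70% with 22 v 23 PCPs, the observed direction is right about 92% of the time, yet a Newcombe interval excludes zero in only 28% of samples, and in those the average absolute difference is 37 points against a true 20.

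The cost is two clauses of text, a little more analysis and fewer suggestive subgroup statements. No new data or participants are needed.
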